3.2.1 Sample Size Considerations

The study planned to enroll up to 36 subjects to ensure 20 subjects in the Primary Endpoint Analysis Set (Section 5.1). The sample size was determined for the purpose of the study without a formal statistical null hypothesis.

At the time of Primary Endpoint Analysis, it was determined to close enrollment with 16 subjects meeting the Primary Endpoint Analysis Set criteria.

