4. STUDY ENDPOINTS AND DEFINITIONS

4.1 Primary Efficacy Endpoint

The primary endpoint is the AIS grade at the 6 month follow-up visit. Improvement in AIS grade of one or more levels (i.e. a grade of B, C, D, or E) at the 6 month follow-up visit will be considered a success.

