5.1 Analysis Populations

The following analysis populations will be prepared for this study:

Screened Set:

The screened population will include all subjects who signed the informed consent form and were screened for participation in this study. This population will be used when describing disposition throughout the study.

Safety Set:

The Safety Set includes all enrolled subjects (i.e. subjects who have signed an Informed Consent Form) that passed the screening assessments. The Safety Set will serve as the analysis set for listings, where data will be presented stratified by screen failures and non-screen failures (as designated by the subject status eCRF page, determined by eligibility procedures at the Screening visit and surgery).

Safety Set Excluding Screen Failure Subjects:

A subgroup of the Safety Set, "Safety Set Excluding Screen Failures" will be considered the subjects in the safety set, but excluding subjects identified as screen failures on the subject status eCRF page. This set will be used for safety table summaries.

All Treated Analysis Set:

The All Treated Analysis Set includes all subjects who have a successful Scaffold implant. The All Treated Analysis Set will serve as the analysis set for all efficacy endpoints.

Primary Endpoint Analysis Set:

The Primary Endpoint Analysis Set includes all subjects who have a successful Scaffold implant, no major protocol deviations that affect data quality, and who have completed the 6-month Primary Endpoint Follow-up Visit. The Primary Endpoint Analysis Set will serve as the analysis set for the primary efficacy endpoint.

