6.2.1 Primary Endpoint Analysis

The Primary Endpoint Analysis will be performed when the 16th subject in the Primary Endpoint Analysis completes the 6-month post-implantation visit.

The primary endpoint analysis is the proportion of subjects from the Primary Endpoint Analysis Set who have an improvement of at least 1 grade on AIS assessment at the 6-month Primary Endpoint Follow-up Visit. The number and percent of subjects with an improvement of at least 1 grade on AIS assessment will be presented. If the proportion of subjects who demonstrate an improvement of at least 1 grade on AIS is at or above 25% the study will be deemed a success using this preset Objective Performance Criterion (OPC) of $\geq 25\%$ as a measure of success.

The primary endpoint analysis will also be conducted utilizing the All Treated Analysis Set. This analysis will be performed in the same manner as described above as a confirmatory analysis. In addition, a sensitivity analysis will be performed that will impute a value for any missing AIS grade at the 6-month Primary Endpoint Follow-up Visit. Any subject who does not have a 6-month Primary Endpoint Follow-up Visit for any reason including premature study withdrawal, will have the primary endpoint imputed to not having an improvement of at least 1 grade on AIS assessment at the 6-month Primary Endpoint Follow-up Visit unless they were assessed as AIS C or better at the last two study visits.

Additionally, the AIS grade will be tabulated by subject at each visit in the All-Treated Set. The number and percentage of subjects with each AIS grade will be tabulated at each visit.

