9. APPENDICES

9.1 Planned Tables, Listings, and Figures

Table Number	Table Name
Table 14.1.1.1	Summary of Subject Enrollment by Site and Analysis Set – Safety Set Excluding Screen Failure Subjects
Table 14.1.1.2	Reasons for Screen Failures – Safety Set Excluding Screen Failure Subjects
Table 14.1.1.3	Subject Disposition – Safety Set Excluding Screen Failure Subjects
Table 14.1.2	Summary of Protocol Deviations – Safety Set Excluding Screen Failure Subjects
Table 14.1.3	Summary of Demographic and Baseline Characteristics – Safety Set Excluding Screen Failure Subjects
Table 14.1.4	Prior and Concomitant Medications - Safety Set Excluding Screen Failure Subjects
Table 14.2.1.1.1	Primary Efficacy Analysis - Primary Endpoint Analysis Set
Table 14.2.1.1.2	Primary Efficacy Analysis - All Treated Set
Table 14.2.1.1.3	Primary Efficacy Analysis - Sensitivity Analysis
Table 14.2.1.2	AIS Scores - Efficacy Analysis - All Treated Set
Table 14.2.1.3	Number of Subjects Each AIS Grade at Each Post-Implantation Time Point - All Treated Set
Table 14.2.2.1	Neurological Level of Injury - Efficacy Analysis - All Treated Set
Table 14.2.2.2	Subject Neurological Level of Injury (NLI) and Zone of Partial Preservation at Assessment Time Points - All Treated Set
Table 14.2.2.3	Number of Subjects With Changes in Neurological Level Direction from Reference Time Points – All Treated Set
Table 14.2.3.1.1	Subject ISNCSCI Sensory Total Score and Changes from Reference Time Points - All Treated Set
Table 14.2.3.1.2	Mean ISNCSCI Sensory Total Score and Changes from Reference Time Points - All Treated Set
Table 14.2.3.1.3	Number of Subjects With Worsening, No Change, and Improvement In ISNCSCI Sensory Total Score from Reference Time Points - All Treated Set
Table 14.2.3.2.1	Subject ISNCSCI Sensory Light Touch Score Change from Pre-Implantation - All Treated Set
Table 14.2.3.2.2	Subject ISNCSCI Sensory Light Touch Score and Changes from Reference Time Points - All Treated Set
Table 14.2.3.2.3	Mean ISNCSCI Sensory Light Touch Score and Changes from Reference Time Points - All Treated Set
Table 14.2.3.2.4	Number of Subjects With Worsening, No Change, and Improvement In ISNCSCI Sensory Light Touch Total Score from Reference Time Points - All Treated Set
Table 14.2.3.3.1	Subject ISNCSCI Sensory Pin Prick Score Change from Pre-Implantation - All Treated Set
Table 14.2.3.3.2	Subject ISNCSCI Sensory Pin Prick Score and Changes from Reference Time Points - All Treated Set

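### In the month-6 sensitivity analysis a subject who died before month 6 can count as improved, and no planned analysis clearly counts every early loss as a failure

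*SAP*

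**What the plan says.** Section 4.1 of the SAP fixes the endpoint at one time: "The primary endpoint is the AIS grade at the 6 month follow-up visit". AIS B or better at that visit is a success. Section 6.2.1 then sets three analyses.

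- **Primary analysis**, on the Primary Endpoint Analysis Set. The study succeeds if the observed proportion improved is 25% or more. Section 5.1 limits this set to implanted subjects with "no major protocol deviations that affect data quality, and who have completed the 6-month Primary Endpoint Follow-up Visit".
- **All Treated analysis**, done in the same manner and labelled confirmatory (Table 14.2.1.1.2).
- **Sensitivity analysis**, introduced thus: "In addition, a sensitivity analysis will be performed that will impute a value for any missing AIS grade at the 6-month Primary Endpoint Follow-up Visit". Section 9.1 lists it as Table 14.2.1.1.3, "Primary Efficacy Analysis - Sensitivity Analysis", with no analysis set in the title.

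The imputation rule belongs to the third analysis. It applies to "Any subject who does not have a 6-month Primary Endpoint Follow-up Visit for any reason including premature study withdrawal". Such a subject is taken as not improved "unless they were assessed as AIS C or better at the last two study visits". The SAP does not say outright what happens to an excepted subject, but the only sensible reading is that the subject counts as improved. Death is neither named nor excluded.

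Elsewhere, section 5.3 rules out imputation unless otherwise indicated, and section 6 leaves the denominators of percentages to footnotes in the table shells.

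**The concern.** A subject who was AIS C at months 2 and 3 and died in month 4 has no AIS grade at month 6. The rule covers every reason for a missing visit, so this subject meets the exception and is counted as a month-6 improver. The window is also wide. Table 1 schedules ISNCSCI exams at hospital discharge and at months 1, 2, 3 and 6, and the exception sets no minimum follow-up. AIS C at discharge and month 1, followed by death, would be enough.

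This matters because the primary set contains completers only, so a subject lost before month 6 leaves its denominator. Table 14.2.1.1.3 is the only planned analysis with a stated rule for these losses. If that rule can credit a death, and the All Treated denominator is left open, the reader has no result that is certain to count every early loss as a failure. In safety, section 5.3 takes the worst case: missing intensity is tabulated as severe and missing causality as definitely related. The exception departs from that approach.

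**Working it through.** The SAP gives no figure for this analysis, so there is none to reproduce. The check is a count against the 25% line.

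**Inputs**
- Criterion: observed proportion of at least 25%, with no test (sections 6.2.1 and 5.2).
- Completers in the primary set: 16. Section 3.2.1: "it was determined to close enrollment with 16 subjects meeting the Primary Endpoint Analysis Set criteria".
- x = improvers among the 16. Not given; 3, 4 and 5 are tried.
- m = further implanted subjects without a month-6 grade. Not given; 1 to 4 are assumed.
- c = subjects credited as improved under the exception.
- The All Treated Set is taken as 16 + m, that is, no implanted subject with a month-6 grade was left out of the primary set for a major data deviation.

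**Step 1, the formal decision.** 0.25 × 16 = 4, so 4/16 = 25.0% is a success. Nobody in this set lacks the month-6 visit, so the result is the same with or without the exception.

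**Step 2, the sensitivity analysis.** Rate = (x + c)/(16 + m).

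| x | c | m = 1 | m = 2 | m = 3 | m = 4 |
|---|---|---|---|---|---|
| 4 | 0 | 4/17 = 23.5% | 4/18 = 22.2% | 4/19 = 21.1% | 4/20 = 20.0% |
| 4 | 1 | 5/17 = 29.4% | 5/18 = 27.8% | 5/19 = 26.3% | 5/20 = 25.0% |
| 3 | 1 | 4/17 = 23.5% | 4/18 = 22.2% | 4/19 = 21.1% | 4/20 = 20.0% |
| 3 | 2 | not possible | 5/18 = 27.8% | 5/19 = 26.3% | 5/20 = 25.0% |
| 5 | 0 | 5/17 = 29.4% | 5/18 = 27.8% | 5/19 = 26.3% | 5/20 = 25.0% |

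At exactly 4 improvers, one credited subject moves the result from below 25% to 25% or more for each m tried. At 3 improvers one credit is not enough and two are needed. At 5 improvers the result is at or above 25% with no credit.

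**Step 3, does the All Treated analysis already count losses as failures?** Take x = 4.
- If the denominator is all implanted subjects, Table 14.2.1.1.2 shows 4/17 to 4/20, and every loss is already a failure.
- If it is observed grades only, which fits the no-imputation rule in section 5.3, Table 14.2.1.1.2 shows 4/16 = 25.0%, and no planned table is certain to show 4/17 to 4/20.

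The SAP text does not choose between the two.

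**The case against.** The strongest reply is that the rule is mostly strict. Its default is failure. A subject seen at month 6 succeeds with AIS B once, while a subject without that visit needs AIS C or better twice, so a drop-out at stable AIS B is counted as a failure. Carrying forward a repeated, higher-grade conversion for someone who withdrew or missed the visit is a defensible choice. This stands, and it limits the point to death and to the absent all-failure result.

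A credited case would also be visible. AIS grade is tabulated by subject and visit for the All Treated Set, and early withdrawals are tabulated with reasons. In a study of this size a reader could undo the credit. That is true, but it leaves the reader to rebuild a result that the SAP could simply specify. The table shells may also settle the All Treated denominator; the SAP text does not.

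Three stronger readings are tempting and are not supported.
- A reader might infer that a death can help the study meet its success criterion. It cannot: the formal decision uses completers only.
- A reader might infer that the sensitivity result can never fall below the All Treated result. That holds only if the All Treated denominator is all implanted subjects. With observed grades only, uncredited losses take 25.0% down to 23.5% or lower.
- A reader might infer that one credit always crosses the 25% line. Of the counts tried, that happens only at 4 improvers.

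**Conclusion.** The point holds for the sensitivity analysis alone. As written, a subject who died before month 6 after AIS C or better at the last two study visits can count as improved at month 6, and no planned analysis clearly counts all losses before month 6 as failures. The effect on the formal 25% decision is nil. In Table 14.2.1.1.3, at exactly 4 improvers among 16 completers and 1 to 4 further implanted subjects without a grade, one credit changes 23.5% to 20.0% into 29.4% to 25.0%. These counts are assumptions: the SAP reports neither the number of missing subjects nor any such death, and that a credited subject counts as improved is implied rather than stated. The change is worth making because it is specific, removes a favourable bias and is cheap. It is not a threat to the primary result.

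**What to change.** In section 6.2.1, state that a subject who dies before month 6 counts as not improved and is never eligible for the AIS C exception.

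In Table 14.2.1.1.3, show two rows:
- all All Treated subjects as denominator, with every missing month-6 AIS grade counted as not improved;
- the rule with the AIS C credit kept for subjects who withdrew or missed the visit, stating outright that a credited subject counts as improved.

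The cost is one sentence of SAP text and one table row. The downside for the sponsor is that the sensitivity percentage may be slightly less favourable.

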6.2.2 Secondary Efficacy Analysis

6.2.2.1 *Change Neurological Level of Injury*

The Neurological Level of Injury (NLI) at the screening visit, pre-surgery visit, 1-month, 2-months, 3-months, 6-months, 12-months and 24-months will be summarized for the All Treated Set. Observed values and change from the baseline will be presented. The confirmatory ISNCSCI exam performed within 8 hours prior to surgery (pre-surgery ISNCSCI) will be used as baseline visit. The zone of partial preservation will also be presented

6.2.2.2 *Change in ISNCSCI Motor Scores*

The ISNCSCI motor scores, including the Right Side Muscle Motor Score, Left Side Muscle Motor Score, LEMS and Motor Total Score, at the screening visit, pre-surgery visit, 1-month, 2-months, 3-months, 6-months, 12-months and 24-months will be summarized for the All Treated Set. Observed values and change from the baseline will be presented. The confirmatory ISNCSCI exam performed within 8 hours prior to surgery (pre-surgery ISNCSCI) will be used as baseline visit.

Individual Motor Total Score and Change from Baseline will be graphically displayed by visit. The mean Motor Total Score (SD) will also be plotted over time.

6.2.2.3 *Change in ISNCSCI Sensory Scores*

The ISNCSCI sensory scores, including the Light Touch Score, Pin Prick Score, and Sensory Total Score, at the screening visit, pre-surgery visit, 1-month, 2-months, 3-months, 6-months, 12-months and 24-months will be summarized for the All Treated Set. Observed values and change from the baseline will be presented. The confirmatory ISNCSCI exam performed within 8 hours prior to surgery (pre-surgery ISNCSCI) will be used as baseline visit.

Individual Sensory Total Score, Light Touch Score, and Pin Prick Score and their Changes from Baseline will be graphically displayed by visit. The mean Sensory Total Score (SD) will also be plotted over time.

6.2.2.4 *Change in Spinal Cord Anatomy*

MR Images (axial and sagittal T1 and T2-weighted images at minimum) are obtained at Screening and 72-hours, 3-months, 6-months, 12-months, and 24-months post-implant. Characteristics of spinal cord anatomy will be assessed by a Board-certified neuroradiologist central reader and will include the following analyses: spinal cord dimensions (above, at, and below level of injury), lesion size and location, cyst presence or absence including size and location, if present. Observed values at 72 hours post-implant and change (in Edema size, Hemorrhage, scaffold detection, cyst and spinal cord adhesion) from baseline will be presented. The Screening MRI will be used as the baseline. These analyses will be performed on the All Treated Analysis Set.

The following will be tabulated by subject at the baseline and 72 hour time points:

- Edema location
- Edema - Sagittal Plane Superior-Inferior (millimeters [mm]), with change from baseline
- Hemorrhage location
- Hemorrhage - Sagittal Plane Superior-Inferior (mm), with change from baseline
- Scaffold Detection at 72 hours (Yes/No)

The following will be tabulated by subject for the 3 Month Visit, 6 Month Visit, 12 Month Visit, and 24 Month Visit:

- Presence of cyst (Yes/No)
- Cyst location
- Cyst size - Sagittal Plane x Axial Plane (mm)
- Spinal Cord Adhesion (Yes/No)
- Spinal Cord Adhesion Location

6.2.3 **Exploratory Analysis**

6.2.3.1 *Change in Bowel Function*

Bowel function will be assessed using the questionnaire from the International Spinal Cord Injury Data Sets – Bowel Function Basic Data Set – Data Form. The following bowel function assessments will be summarized in descriptive tables by subject and for the overall

population at each time point (1-month, 2-months, 3-months, 6-months, and 12-months post-Scaffold implantation):

- 1) Subjects with awareness of the need to defecate
- 2) Main method for bowel defecation and bowel care procedure
- 3) Supplementary method for bowel defecation and bowel care procedure
- 4) Average time required for defecation and frequency of defecation
- 5) Frequency of fecal incontinence
- 6) Need to wear pad or plug
- 7) Use of laxatives and use of medication affecting bowel function/constipating agents
- 8) Perianal problems since last visit

Observed values and any changes of baseline (1-month post-implantation) will be assessed qualitatively. If data warrants additional exploratory work may be carried out to gain a better understanding of subject characteristics and the degree of improvement.

6.2.3.2 *Change in Bladder Function*

Bladder function will be assessed using the questionnaire from the International Spinal Cord Injury Data Sets – Lower Urinary Tract Function Basic Data Set – Data Form. The following bladder function assessments will be summarized in descriptive tables by subject and for the overall population at each time point (1-month, 2-months, 3-months, 6-months, and 12-months post-Scaffold implantation):

- 1) Number of subjects reported yes to question of ‘Awareness of the need to empty bladder (yes/no)’ at each time point.
- 2) Frequency of major bladder emptying methods at each time point
- 3) Frequency of supplementary bladder emptying methods at each time point
- 4) Distribution of average number of voluntary bladder-emptying per day at each time point
- 5) Distribution of subjects with any involuntary urine leakage at each assessment time points
- 6) Distribution of subjects taking medications for urinary tract

7) Distribution of subjects with surgical procedures on urinary tract and list of type of surgery at each time point

Observed values and any changes of baseline (1-month post-implantation) will be assessed qualitatively. If data warrants additional exploratory work may be carried out to gain a better understanding of subject characteristics and the degree of improvement.

6.2.3.3 *Change in Sexual Function*

Sexual function will be assessed using the International Spinal Cord Injury Male and Female Sexual Function Basic Data Sets (version 2.0). The sexual function assessments are designed to record data on sexual function for individuals with spinal cord lesions, and to standardize the collection and reporting of information on sexual function in daily practice.

The site will interview the subject on various aspects of their sexual function, including their interest in discussing sexual issues and any sexual dysfunction related to the spinal cord injury, and will complete the required assessments.

Sexual function will be assessed prior to hospital discharge and at post-Scaffold implant study visits at 1, 2, 3, 6 and 12-months.

Due to no sexual data collected at the time of the Primary Endpoint Analysis, Sexual Function will be presented only after the Long-term Follow-up Period of all subjects has been completed.

6.2.3.4 *Change in Pain*

Pain will be assessed at all study visits beginning at Hospital Discharge through the 12 Month Long-Term Follow-up Visit using the International Spinal Cord Injury Pain Basic Data Set Data Collection Form Version 2.0 (Appendix G of the protocol). Pain assessment findings by time profile will be prepared for each subject. Pain assessments at the hospital discharge will be used as the reference time point for the assessment of change in pain intensity.

There are 3 pain assessments at each time point: worst, second worst, and third worst pain assessments. However, pain assessments will focus on the worst pain problems that a subject had during the last 7 days. The following pain assessments will be tabulated by subject and summarized:

- Reported pain score for the worst pain at each time point. A subject's pain score at a given time point is the average pain intensity reported by the subject during the worst

pain assessment at that time point, where a lower score corresponds to less pain (i.e. lower score corresponds to improvement).

- Number of pains reported by subject (0 to ≥ 5) at each time point, where fewer reported pains are better
- Reported quality of life scores at each time point for pain “interferes with activities,” “interferes with mood,” and “interferes with sleep” (0 to 10), where a lower score corresponds with a higher quality of life (i.e. lower score corresponds to improvement).

The number of subjects with improvement, worsening, and no change in pain assessments will be tabulated.

Worst pain scores and quality of life scores will be plotted by individual and by mean over time.

6.2.3.5 *Change in SCIM III*

The Spinal Cord Independence Measure (SCIM) III will be assessed (Appendix I of the protocol) at discharge and at months 1, 2, 3, 6, and 12. SCIM III results at discharge will be used as the reference time point (baseline) to assess changes in subjects’ quality of life at months 1, 2, 3, 6, and 12. The Spinal Cord Independence Measure (SCIM) III covers 19 tasks, all activities of daily living, grouped into four areas of function: Self-Care (Questions 1-4, scored 0-20), Respiration and Sphincter Management (Questions 5-8, scored 0-40), Mobility in Room and Toilet (Questions 9-11) and Mobility Indoors and Outdoors on Even Surface (Questions 12-17) (Mobility Questions 9-17, Scored 0-40). The final total SCIM III is the sum of all scores and ranges from 0 to 100, with 0 being requiring total assistance and 100 being completely independent.

SCIM III total score and each domain score will be calculated for each subject at hospital discharge and at months 1, 2, 3, 6, and 12. Change from baseline (Hospital Discharge) in SCIM III will also be derived at each post baseline time point. SCIM III total score, scores for each area of function, change from baseline for total score and functional score will be tabulated by subject and summarized overall at each time point. Additionally, the scores for sphincter management – bladder and bowel (out of 15 and out of 10, respectively) and the change from baseline will be tabulated by subject over time and summarized at each time point.

Subjects with improvement, worsening, and no change from baseline in their quality of life as determined by their SCIM III assessments will be tabulated. Improvement will be defined as an increase in SCIM III score/subscore from baseline, while worsening will be defined as a decrease in score/subscore.

SCIM III total individual and mean scores (with SD) will be plotted over time.

